## **2 Study Objectives and Design**

### **2.1. Study Objectives**

The overall aim of this study is to investigate the role of autobiographical episodic memory impairments in experiential negative symptoms and depression in people with schizophrenia.

First, cross sectional associations between these constructs will be examined using the currently available most valid measures of these constructs and including the measurement of possible confounders including cognition and self-efficacy.

Second, an intervention study will be conducted to further explore the potential causal mechanism of autobiographical episodic memory in negative symptoms. This will use a brief intervention targeting memory flexibility hypothesised to improve pleasure and motivation outcomes.

### **2.2 Study Design**

A single sample of participants will be recruited for the two parts of the study. Part 1 will have a cross-sectional design with the aim of examining hypothesised relationships between autobiographical memory and experiential negative symptoms. Part 2 will have an experimental design and the participants will be randomized to either the intervention or control condition with a randomization ratio of 2:1.

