## Study Synopsis

[figure not shown]
Full Title	Is there a Relationship between Memory for Past Events and Motivation for Future Activities?
Short Title/Acronym	The Relationship between Autobiographical Memory and Motivation
Protocol Version number and Date	V4 14/11/16
Study Duration	27 months
Study Design	A cross-sectional, experimental study with a pilot intervention study component.
Sponsor/Co-sponsors	South London and Maudsley NHS Trust
Chief Investigator	[name]
REC number	
Primary objective	Cross sectional associations between autobiographical episodic memory, motivation, experience of pleasure and depression will be examined.
Secondary objective (s)	An intervention study will be conducted to further explore the potential causal role of autobiographical episodic memory in experiential negative symptoms. This will use a brief intervention targeting memory flexibility which is hypothesised to improve pleasure and motivation outcomes.
Number of Subjects	35-40
Main Inclusion Criteria	A diagnosis of non-affective psychosis (as determined by medical records). Aged 18-65yrs. A score of at least 18 on the Clinical Assessment Interview for Negative Symptoms. A good command of the English language.
Statistical Methodology and Analysis	Correlational analyses will be conducted to examine the relationships hypothesised in Part 1 of the study. The ratings provided before and after the study will be analysed in a between-groups ANOVA to assess the effect of the brief intervention on mood, motivation, anticipatory pleasure and self-efficacy beliefs.

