## **3. Sample Size, Statistics, Selection and Withdrawal of Subjects**

People with a diagnosis of non-affective psychosis aged 18 - 65yrs will be recruited from local community mental health teams and inpatient wards within South London and Maudsley NHS Trust. Further eligibility criteria for the study are a score of at least 18 on the experiential subscale of the Clinical Assessment Interview for Negative Symptoms to ensure at least a moderate level of current negative symptomatology.

A power analysis conducted in GPower Software (version 3.2) with power at 0.8 and  $\alpha = 0.05$  found a sample size of 32 would be sufficient to replicate a correlation with a medium effect size of 0.43 between memory specificity and negative symptoms reported by Harrison and Fowler (2004). To account for drop-outs a sample size of 35-40 will be recruited, if there are few drop-outs this will also increase the power of the study. This sample size with a randomisation ratio of 2:1 is sufficient to detect an F statistic of 0.43 with power at 0.8 and 0.53 with power at 0.9.

There will be three recruitment routes in the study;

1. If recruited through a clinical team then the participant will first be approached by a member of their care team to introduce the study. If they indicate that they are happy to consider the project and give verbal consent for the researcher to contact them then they will be provided with the information sheet. The researcher will then contact them again after at least 24 hours to discuss their potential participation.
2. If recruited through CRIS then potential participants will first be approached by the researcher. This will be done by phone or letter, depending on the preference indicated by the potential participant.
3. If recruited through a recruitment poster then the participant will contact the researcher using the details provided on the poster.

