### **Procedure**

Part 1: Participants will complete the baseline autobiographical memory task which involves recalling 1 positive and 1 negative event which will be audio-recorded and coded by two independent raters. Then participants will complete the two subtests of the Wechsler Abbreviated Intelligence Scale - verbal fluency and letter-number sequencing which assess working memory. Two questionnaires that assess depression symptoms and negative thinking (Beck Depression Inventory and Dysfunctional Attitudes Scale) will then be completed by the participant. Finally, three interviews assessing symptoms and functioning will be conducted by the researcher (CAINS, Time Use Survey and Scale for the Assessment of Positive Symptoms (SAPS). This session should last approximately 1.5-2hrs.

Part 2: After Part 1 the participants will be randomized to the intervention or control group using a 2:1 ratio and the “sealed envelope” online software. This will be done by the Chief Investigator who will record the randomisation process and outcome. At the start of the Part 2 session the participants will be asked to select a positive event to describe. They will then complete the visual analogue scales assessing positive and negative feelings, motivation, anticipatory pleasure and self-efficacy. The participants will then complete either the intervention or control task before repeating the visual analogue scales again. The intervention and control task both involve describing this positive event; the control task with no prompts and the intervention task with prompts and videos encouraging them to include more detail in their recall and to link it to past and future events as well. Participants will do this process for two positive events and this session should last approximately 1 hr. Participants will be asked to complete a brief feedback questionnaire at the end of their participation in the study.

This concludes the participant’s involvement in the research.

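### Part 2 pairs an unexplained 2:1 allocation with an equal-variance ANOVA: the test needs an unequal-variance form, and the ratio needs a stated reason or should be 1:1

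*Combined protocol and SAP*

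**What the plan says.** Section 2.2 (Study Design) uses one sample for both parts and sets the Part 2 ratio: "the participants will be randomized to either the intervention or control condition with a randomization ratio of 2:1". The Procedure text in Section 4 repeats it: "After Part 1 the participants will be randomized to the intervention or control group using a 2:1 ratio". Neither place explains the choice.

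The total comes from Part 1. Section 3 "found a sample size of 32 would be sufficient to replicate a correlation with a medium effect size of 0.43", and then adds a margin: "To account for drop-outs a sample size of 35-40 will be recruited". For Part 2, Section 3 says the resulting sample at 2:1 "is sufficient to detect an F statistic of 0.43 with power at 0.8 and 0.53 with power at 0.9". The ratio was therefore carried into the power statement, but it is not justified there.

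The Synopsis says the before and after ratings "will be analysed in a between-groups ANOVA to assess the effect of the brief intervention". It does not say whether this is a test on change scores, a group-by-time model or a baseline-adjusted model, and it mentions no allowance for unequal variances. The Synopsis also labels Part 2 a pilot component and places it under the secondary objective.

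**The concern.** Two issues meet here and should be kept apart.

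The first is the analysis. An ordinary ANOVA pools the variance of the two arms. With equal arms that does little harm if the spreads differ. With one arm twice the size of the other, the pooled variance is dominated by the larger arm, so the standard error is wrong in a direction that depends on which arm is more variable. The outcomes are bounded visual analogue ratings, and one arm is prompted while the other is not, so equal spread after the task should not be taken for granted.

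The second is the allocation. Because Part 1 fixes the total and uses everyone, the Part 2 ratio has no bearing on Part 1. It only divides a fixed number of people between the arms, and with equal SDs an uneven split gives a less precise comparison. Part 2 is the only randomised test of the proposed causal mechanism, so both its error rate and its precision matter.

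**Working it through.** **Inputs.** Ratio 2:1 (Sections 2.2, 3 and Procedure); N = 35 to 40, alpha 0.05 with sidedness not stated, and effects of 0.43 and 0.53 (Section 3). I take whole-number splits of 23/12 at N = 35 and 27/13 at N = 40. Assumptions: the stated effect is Cohen's f, so d = 2f = 0.86 and 1.06; SD ratios of 1.25, 1.5 and 2.

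**1. The plan's own figure.** Power is from the noncentral t distribution with noncentrality d × √(n1·n2/N). One-sided at 25/13 (N = 38), power is 79.5% for f = 0.43 and 91.9% for f = 0.53, close to the stated 0.8 and 0.9. Two-sided, it is 68.7% and 85.5%. On this reading the stated power is a one-sided figure. That is a separate matter; the comparisons below are two-sided.

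**2. Why the pooled test fails at 27/13.** Take an intervention SD of 1 and a control SD of 1.5.
- True variance of the difference: 1/27 + 2.25/13 = 0.210.
- Average pooled estimate: (26×1 + 12×2.25)/38 × (1/27 + 1/13) = 1.395 × 0.1140 = 0.159, which is too small.
- With the SDs reversed: true 2.25/27 + 1/13 = 0.160; pooled (26×2.25 + 12×1)/38 × 0.1140 = 0.211, which is too large.
- At 20/20 both expressions give 3.25/20 = 0.1625.

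**3. Type I error** (simulation with normal data, 400,000 replicates, nominal two-sided 5%):

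| Larger SD / smaller SD | Pooled 27/13, control larger | Pooled 27/13, intervention larger | Pooled 20/20 |
|---|---|---|---|
| 1.25 | 7.0% | 3.4% | 5.1% |
| 1.5 | 8.8% | 2.6% | 5.1% |
| 2 | 11.7% | 1.7% | 5.2% |

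Welch's test at 27/13 stays between 4.9% and 5.1% in every row. If the ANOVA is a group-by-time model with two time points, its interaction test is the pooled test on change scores, so the table applies to it as well.

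**4. Price of Welch.** With equal SDs at 27/13 and d = 0.86, power goes from 69.9% to 68.3%, a loss of about 1.6 points.

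**5. Price of 2:1 with equal SDs.** Relative information is 4 × (2/3) × (1/3) = 8/9, so 40 people at 2:1 are worth 40 × 8/9 = 35.6 at 1:1. The loss is 9.8% to 12.3% at the actual whole-number splits. Two-sided power:

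| N | d | 2:1 | 1:1 |
|---|---|---|---|
| 35 (23/12 v 18/17) | 0.86 | 65.0% | 69.4% |
| 40 (27/13 v 20/20) | 0.86 | 69.9% | 75.5% |
| 35 | 0.912 | 70.1% | 74.5% |
| 40 | 0.912 | 75.0% | 80.3% |

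The lower rows use d = 0.43/√(2/9) = 0.912, which applies if f was defined on the 2:1 weights. At N = 40 the 95% half-width for the arm difference falls from 0.68 to 0.64 SD.

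**6. What 1:1 gives up.** The intervention arm shrinks from 27 to 20 at N = 40. The 95% half-width for a within-arm mean change is t/√n: 2.056/√27 = 0.40 SD against 2.093/√20 = 0.47 SD.

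**The case against.** Part 2 is a labelled pilot, and placing more people on a new intervention is a legitimate choice in a pilot. The protocol has uses for a larger intervention arm. The Intervention section compares narratives produced during the intervention with the baseline task, and the Feedback Questionnaire asks which elements helped. If the narrative comparison is made within the intervention arm, 1:1 widens its interval by about 18% (0.40 to 0.47 SD), while the between-arm interval narrows by about 6% (0.68 to 0.64 SD). This stands: moving to 1:1 is a trade, although the protocol does not offer this as its reason for 2:1.

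The error-rate problem is also not an argument for 1:1, since Welch's test deals with it at 27/13. This stands too, and it is why the two issues are separated here.

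The 8/9 figure assumes equal SDs. With intervention SD s1 and control SD s2, the variance of the difference is (1.5·s1² + 3·s2²)/N at 2:1 and (2·s1² + 2·s2²)/N at 1:1. These are equal at s1/s2 = √2 = 1.41, and beyond that 2:1 is the more precise. At N = 36 with an SD ratio of 1.5 (d = 0.86 in average-SD units), the planned pooled test would still have less power at 2:1 (61.5% against 70.8%), but Welch's test would be about level (71.1% against 70.3%).

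Finally, a reader might infer that the ratio explains why two-sided power falls below the stated 0.8. It does so only in part. At 27/13 and d = 0.86, going from one-sided to two-sided takes power from 80.4% to 69.9%, about 10.5 points; changing the ratio returns 5.6.

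**Conclusion.** The point holds in two parts of different strength.

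The firmer part is the analysis. At about 27/13 the planned equal-variance ANOVA has a type I error that can run from about 1.7% to 12% over SD ratios up to 2, and already from 3.4% to 7% at 1.25. An unequal-variance test removes this at little cost. The documents give no SDs, so a reader should not infer that the error rate will be inflated. It is unprotected, and the direction is unknown.

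The second part is the ratio. With equal SDs, 2:1 costs about 11% of the information and about 4 to 6 points of two-sided power, for a reason the protocol does not state. It is tempting to call 2:1 an error, or 1:1 a free gain. The documents support neither: the pilot label, the narrative comparison and the feedback questionnaire are all plausible uses for a larger intervention arm. Without a stated reason, 1:1 is the better default for the between-arm comparison.

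**What to change.** **Analysis (Synopsis and Section 3), at either ratio.** Replace the unspecified ANOVA with Welch's test on the difference between arms in change scores, or with a baseline-adjusted linear model using HC3 standard errors. State that the test is two-sided. Welch's test costs about 1.6 points of power if the SDs are in fact equal; the corresponding cost for the HC3 model was not calculated here.

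**Allocation (Sections 2.2, 3 and Procedure, and the online randomisation set-up).** Change to 1:1, or keep 2:1 and add a sentence giving the reason and accepting the loss of precision. If 1:1 is adopted, restate the Part 2 detectable effect. At 80% power, two-sided with equal SDs, it is d = 0.98 at N = 35 and 0.91 at N = 40. If 2:1 is kept, the matching values are 1.03 and 0.97.

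The cost is wording and one randomisation setting, with no extra participants and no effect on Part 1. At N = 40, 1:1 means about 7 fewer people receiving the intervention, so less feedback on it and a less precise within-arm narrative comparison.

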## **3. Sample Size, Statistics, Selection and Withdrawal of Subjects**

People with a diagnosis of non-affective psychosis aged 18 - 65yrs will be recruited from local community mental health teams and inpatient wards within South London and Maudsley NHS Trust. Further eligibility criteria for the study are a score of at least 18 on the experiential subscale of the Clinical Assessment Interview for Negative Symptoms to ensure at least a moderate level of current negative symptomatology.

A power analysis conducted in GPower Software (version 3.2) with power at 0.8 and  $\alpha = 0.05$  found a sample size of 32 would be sufficient to replicate a correlation with a medium effect size of 0.43 between memory specificity and negative symptoms reported by Harrison and Fowler (2004). To account for drop-outs a sample size of 35-40 will be recruited, if there are few drop-outs this will also increase the power of the study. This sample size with a randomisation ratio of 2:1 is sufficient to detect an F statistic of 0.43 with power at 0.8 and 0.53 with power at 0.9.

There will be three recruitment routes in the study;

1. If recruited through a clinical team then the participant will first be approached by a member of their care team to introduce the study. If they indicate that they are happy to consider the project and give verbal consent for the researcher to contact them then they will be provided with the information sheet. The researcher will then contact them again after at least 24 hours to discuss their potential participation.
2. If recruited through CRIS then potential participants will first be approached by the researcher. This will be done by phone or letter, depending on the preference indicated by the potential participant.
3. If recruited through a recruitment poster then the participant will contact the researcher using the details provided on the poster.

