### **Part 2 Experimental Study**

## **Outcomes**

The participants will be asked to rate the following items before and after their participation in either the intervention or control condition. These are rated on 100-point visual analogue scales from 1 “Not at All” to 10 “Very Much So”. These are similar to those used in experience sampling studies where these repeated measures have been shown to be reliable and valid (Gard, Kring et al. 2007, Oorschot, Lataster et al. 2011, Gard, Sanchez et al. 2014).

- 1) Right now I feel [enthusiastic, satisfied, relaxed, cheerful]
- 2) Right now I feel [down, guilty, anxious, annoyed]
- 3) How likely the event is to happen again.
- 4) How able they would feel to engage in the future event.
- 5) How enjoyable the future event would be.

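### The Part 2 power figures do not match the between-groups ANOVA that the plan names: at f = 0.43 its two-sided test has 69.5% to 75.5% power with 35 to 40 participants, not 80%

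*Combined protocol and SAP*

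**What the plan says.** Section 3 justifies the sample size in two steps. Part 1 needs 32 participants for a correlation of 0.43 at 80% power and alpha 0.05. Then: "To account for drop-outs a sample size of 35-40 will be recruited". For the randomised comparison it takes the same number of participants, allocated two to one, and states that this "is sufficient to detect an F statistic of 0.43 with power at 0.8 and 0.53 with power at 0.9".

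The analysis appears only in the Study Synopsis: "The ratings provided before and after the study will be analysed in a between-groups ANOVA". Under Outcomes, participants are "asked to rate the following items before and after their participation in either the intervention or control condition". The Procedure section confirms the order: "The participants will then complete either the intervention or control task before repeating the visual analogue scales again". It also has each participant do this for two positive events.

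The plan does not say how the before and after ratings enter the ANOVA, whether the test is one- or two-sided, how many participants will be analysed in Part 2 after drop-outs, or to which standard deviation f is scaled. Alpha is given only in the Part 1 sentence. The hypothesis is directional: the intervention is "hypothesised to improve pleasure and motivation outcomes".

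**The concern.** This sentence is the only power claim for the randomised comparison. A reader who puts its numbers into the test that the synopsis names does not get 80% power at any sample size in the stated range. A null result would then be read against a sensitivity that the named test does not have. The label adds to the difficulty: an F statistic of 0.43 is a test result, and not an effect that a study can be sized to detect.

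**Working it through.** **Inputs from the plan.** N = 35 to 40; 2:1 allocation; effects 0.43 and 0.53, read as effect size f; target powers 80% and 90% (all Section 3). Alpha 0.05 is carried over from the Part 1 sentence. The model is a two-group between-groups ANOVA (Study Synopsis).

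**Reading tested.** One score per participant, for example the after-minus-before change, with f scaled to the SD of that score. The F test has 1 and N − 2 degrees of freedom and noncentrality λ = f²N. Power is the probability that a noncentral F exceeds the central 95% point.

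**Example.** N = 35, f = 0.43: λ = 0.1849 × 35 = 6.47; critical F(1, 33) = 4.14; power 69.5%. N = 40: λ = 7.40; critical F(1, 38) = 4.10; power 75.5%.

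| N | Power at f = 0.43 | Power at f = 0.53 |
|---|---|---|
| 32 | 65.3% | 82.7% |
| 35 | 69.5% | 86.1% |
| 36 | 70.8% | 87.1% |
| 37 | 72.0% | 88.0% |
| 38 | 73.2% | 88.9% |
| 39 | 74.4% | 89.7% |
| 40 | 75.5% | 90.4% |
| 44 | 79.6% | 93.0% |
| 45 | 80.5% | 93.5% |

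The 80% figure is missed at every N from 35 to 40. The 90% figure is met only at N = 40. Solving for f instead gives:

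| N | Detectable f, 80% power | Detectable f, 90% power |
|---|---|---|
| 35 | 0.488 | 0.565 |
| 40 | 0.455 | 0.526 |

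**Can the plan's figures be reproduced?** Yes, with a one-sided 0.05 test (noncentral t, N − 2 df, noncentrality f√N). At N = 35 power is 80.1% at f = 0.43 and 92.3% at f = 0.53; at N = 40 it is 84.8% and 95.0%. The one-sided detectable f is 0.429 at 80% power with N = 35, and 0.529 at 90% power with N = 32.

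**Cross-check on Part 1.** For r = 0.43, Fisher's z is 0.460, and 0.460 × √29 = 2.48 at N = 32. Power is about 79.7% one-sided (cut-off 1.645) and 69.7% two-sided (cut-off 1.96). The Part 1 sample size of 32 therefore also fits only a one-sided test.

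**Do the two Part 2 figures belong together?** At one N and one alpha, the detectable f at 90% power is 1.157 times that at 80% for a two-sided test, and 1.177 times for a one-sided test. The stated ratio is 0.53/0.43 = 1.23, or at least 0.525/0.435 = 1.207 allowing for rounding. So on these two readings they cannot both be the smallest detectable effects at the same N.

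**Other models.** The plan gives no before–after correlation ρ, so ρ is an assumption here and the range is shown. Two ratings per participant, two-sided 0.05:

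| Model | Multiplier on λ | Both targets met at N = 35 | Both targets met at N = 40 |
|---|---|---|---|
| Repeated measures, group main effect | 2/(1 + ρ) | ρ ≤ 0.55 | ρ ≤ 0.78 |
| Baseline-adjusted (N − 3 df) | 1/(1 − ρ²) | ρ ≥ 0.48 | ρ ≥ 0.33 |
| Change score, f on the single-rating SD | 1/(2(1 − ρ)) | ρ ≥ 0.62 | ρ ≥ 0.56 |
| Time-by-group interaction, f on that term | 2/(1 − ρ) | any ρ ≥ 0 | any ρ ≥ 0 |

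These rows do not describe the same effect. At 2:1 the standardised difference is d = f/√(2/9), so f = 0.43 is 0.91 SDs on the single-rating scale. An interaction f of 0.43 has the same noncentrality as a single-rating f of 0.86, and 0.86/√(2/9) = 1.82 single-rating SDs.

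**The case against.** The strongest reply is that the authors probably worked one-sided. Section 3 supports this: the Part 1 sample size fits only a one-sided test, the same convention reaches 80% at f = 0.43 from N = 35, the bottom of the recruitment range, and the hypothesis is directional. That is a plausible account of where the figures came from. But it is an inference: no sentence declares a one-sided test, and the F test of the named ANOVA is non-directional. One-sided testing also leaves the drop-out question open. If only 32 are analysed, one-sided power is 76.8% at f = 0.43 and 90.05% at f = 0.53.

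The second reply is that one score per participant is not the only natural reading. Ratings are taken before and after, for two events. With an assumed correlation of 0.5, a repeated-measures group main effect has 81.4% to 86.4% power at f = 0.43 with two ratings, and 87.8% to 91.8% with four. This stands as a possibility, although a main effect pooled over time is not the most direct test of a treatment effect. It depends on a correlation that the plan does not give.

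A reader might therefore infer too much in one of two ways: that the power figures are an arithmetic error under any reading, or that the plan names no model at all. The documents support neither. Several readings meet the figures, and the synopsis does name the model family.

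**Conclusion.** The stated power and the named analysis do not agree. For a two-sided between-groups ANOVA on one score per participant at alpha 0.05, the shortfall at f = 0.43 is 4.5 points (80 − 75.5, N = 40) to 10.5 points (80 − 69.5, N = 35). The 90% figure holds only at N = 40. This rests on reading the F statistic as effect size f, on carrying alpha 0.05 over from Part 1, and on scaling f to the analysed score.

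The figures look like undeclared one-sided power and not a slip in calculation. A reader might also infer that the study must recruit 45. That does not follow, since the remedy is to state the right detectable effect for the planned numbers. Severity is minor: the synopsis describes "A cross-sectional, experimental study with a pilot intervention study component", and the randomised comparison is a secondary objective.

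**What to change.** In Section 3, make the power sentence match the test that will be run.

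- If that is the two-sided between-groups ANOVA on one score per participant (for example the change score, with f on that score's SD), restate the detectable effect size f as about 0.49 (N = 35) to 0.455 (N = 40) at 80% power, and about 0.565 to 0.53 at 90% power. Add that power falls if drop-outs reduce the analysed number: with 32 analysed it is 65.3% at f = 0.43 and 82.7% at f = 0.53.
- If a one-sided test, or a repeated-measures or baseline-adjusted model, is intended, say so. Give the figures for that test, with the SD to which f is scaled and any assumed before–after correlation.
- In either case, replace the label F statistic with effect size f.

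The cost is one or two sentences and, on the two-sided reading, a slightly less favourable stated figure. No extra participants and no change of design are needed.
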